## **II. Overall Study Objective**

The **overall objective** of this study is to evaluate the ability of HVNI next generation Prosoft nasal cannula designs to effect ventilation and related physiological responses relative to the conventional legacy cannula design, with which there are published clinical outcomes data.

The **hypothesis**: The next generation nasal cannula designs (Prosoft and Unicorn) will be comparable at relieving patient dyspnea while on HVNI, when compared to the conventional legacy cannula.

To test this hypothesis, the study will be conducted with the following specific aims:

Aim #1: Primary Outcome. The primary endpoint is the patient's targeted relief of dyspnea, as measured by the modified Borg scale (rated perceived dyspnea [RPD]) for each cannula design tested.

Aim #2: Secondary Outcomes. The secondary endpoints evaluate the patient vital signs (heart rate [HR], respiratory rate [RR], blood pressure [BP]), arterial oxygen saturation (SpO2), and arterial CO2 as measured by a transcutaneous CO2 device (TcPCO2). These measurements will be compiled for each cannula design tested.

Aim #3: Tertiary Outcomes. The tertiary endpoints evaluate both patient and clinician perception assessment scores. For patient perception/satisfaction these endpoints include: (1) relief of symptoms, and (2) comfort/tolerance. For clinician perceptions these endpoints include: (1) technical/clinical difficulties, (2) patient comfort & tolerance, (3) ease of use, (4) monitoring & support for therapy, and (5) expected/perceived patient outcomes.

These **endpoints** will establish equivalence of outcomes between the legacy cannula and the new cannula designs (both Unicorn and Prosoft) in terms of the ability to relieve dyspnea in adult hypercapnic patients experiencing dyspnea.

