## Sample Size:

To provide a sufficiently powered sample dataset, we will enroll up to 32 subjects to complete this study on nasal cannula designs, with a calculated sample size of N=26 plus a 20% failure/fallout rate. This will provide sufficient data to adequately inform on the study objectives.

This sample size was estimated through use of references that (1) approximated minimal clinical important difference of dyspnea (modified Borg scale) and (2) approximated expected standard deviation of prior datasets measuring dyspnea. Estimated minimal clinical important difference of dyspnea was determined to be a difference value of 2 in modified Borg for dyspnea. In reviewing publications from Roca 2010 and Schwabbauer 2014, it was estimated that a value of 2 to 3 was suitable for the standard deviation of dyspnea for the modified Borg scale. Therefore, for this study, using the paired t-test sample size calculation, with an expected difference of 2, and an expected standard deviation of 3, using a desired power of 90% with alpha=0.05, the sample size is estimated at 26 to show if the data may or may not have any difference.

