HVNI will be initiated per the initial settings identified below, after which settings will be titrated per standard practice for optimal effect. When patients are placed, the HVNI initial settings will be the following: FiO2 = level approximating the patient's prior prescription (e.g. if by nasal cannula [NC], 1LPM NC = 24%, 2LPM NC = 28%, 3LPM NC = 32%, etc.), Flow = 15 L/min, and Temperature = 35 - 37°C. Patients will be fit with a Vapotherm adult nasal cannula that will be applied by a respiratory therapist or other clinician skilled in management of HVNI. The flowrate can be decreased or increased as rapidly as necessary to alleviate respiratory distress and optimize patient comfort. Targets should be to provide relief of perceived dyspnea at an HVNI flow rate between 20 to 35 L/min (up to 40L/min). Starting temperature will be between 35 to 37°C; if patients find the gas temperature to be uncomfortable, it can be lowered as necessary down to 33 °C to enhance tolerance. The FiO2 will be set initially to approximate the likely previous dosage (see above) to initially to assure adequate oxygenation, but this should be adjusted to maintain a SpO2 > 88%.

Therapeutic Characterization will be performed 5-10 minutes after the therapy acclimatization segment is completed. This will provide the patient sufficient time to receive clinical effect of the HVNI therapy and

become sufficiently comfortable with the therapy and cannula. Once the respiratory therapist or other clinician skilled in management of HVNI deems that the HVNI settings are having a therapeutic effect, the following data will be collected (see Table 1): RR, HR, BP, SpO2, TcPCO2 and RPD (Modified Borg scale 0-10). For the RPD, the clinician will record patient scores.

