## VIII. Statistical Analysis

The data analysis will be "per protocol." Baseline patient demographics and characteristics will be summarized, compared, and appropriate statistical testing will be performed for the continuous and categorical variables. Assuming a non-normal data distribution for this crossover order-randomized study design, the non-parametric Wilcoxon Signed Rank Sum test will be performed with significance interval of 0.05 on all applicable variables. Parametric analytical analogues (e.g. t-test) will be use if the measurements present a normal distribution. Otherwise, for the categorical variables, the Fisher's Exact test will be performed. Data will be compared and graphed accordingly for a visual comparison with accompanied statistical notations.

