## X. Potential Benefits

Subjects may or may not receive any direct health benefit from participation. Due to the short duration of the exposure, it is not likely that the patients enrolled in the HVNI cannula study will themselves benefit from participation in this study. The trial may result in scientific knowledge that leads to improvements in the quality of patient care, patient experience, and the effect cannula designs have on patient dyspnea relief.

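### Comparable relief of dyspnea is to be claimed, but nothing in the analysis plan makes that claim depend on the legacy cannula having relieved dyspnea in this trial

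*Combined protocol and SAP*

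**What the plan says.** Section II states the hypothesis that Prosoft and Unicorn "will be comparable at relieving patient dyspnea while on HVNI, when compared to the conventional legacy cannula". It calls the primary endpoint relief of dyspnea for each cannula, measured by RPD, and closes by saying that the endpoints will establish equivalence. It does not define relief as a change from baseline.

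Section VIII plans Wilcoxon signed-rank tests (or t-tests) at 0.05 on all applicable variables and adds: "Data will be compared and graphed accordingly for a visual comparison with accompanied statistical notations". It names no contrast, equivalence margin or minimum legacy response, and gives no rule for concluding comparability.

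The data for a within-legacy analysis will exist. Section VII has RPD recorded in every segment of every phase, including baseline and therapeutic characterization. Legacy is always Phase 1 (Section IV). The Phase 1 baseline may be taken with the patient already on HVNI (Section VI, Phase 1).

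On whether an effect can be seen in the time allowed, Section VI says of the interval before the therapeutic reading: "This will provide the patient sufficient time to receive clinical effect of the HVNI therapy". Section X says: "Due to the short duration of the exposure, it is not likely that the patients enrolled in the HVNI cannula study will themselves benefit".

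**The concern.** A finding that two treatments relieve a symptom equally has two parts: the scores are alike, and the reference treatment gave relief. The plan addresses only the first. No period is untreated or sham, so the main internal evidence that RPD can respond in this setting is the change from baseline on legacy. If that change were nil, similar scores on all three cannulas would be the expected result of an experiment that could not register relief. Nothing in Section VIII would prevent it from being reported as comparable relief.

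The question is a practical one. The therapeutic reading falls after roughly 10 to 20 minutes on each cannula (5–10 minutes of acclimatization, then 5–10 more). The ratings are subjective and unblinded.

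**Working it through.** **Inputs.** The Sample Size paragraph of Section V gives a paired t-test "with an expected difference of 2, and an expected standard deviation of 3", "using a desired power of 90% with alpha=0.05". It puts the SD in the range 2 to 3 and takes 2 Borg points as the minimal important difference. Assumptions made here: the SD of the within-phase change is also 2 to 3; the illustrative equivalence margin is 2, since the plan states none; errors are normal and independent, so the two contrasts sharing legacy correlate 0.5.

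**Step 1: the plan's own figure.** With effect size 2/3, two-sided alpha 0.05 and 90% power, the paired t calculation gives n = 25.6, so 26. Power at 26 is 90.4%. The figure reproduces. By the plan's wording, "the sample size is estimated at 26 to show if the data may or may not have any difference", it is sized to detect a difference.

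**Step 2: does a margin alone protect the claim?** Suppose all three cannulas do nothing. Two one-sided tests (TOST) pass when |mean difference| + t × SD/√26 < 2.

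- SD 3: the standard error is 3/√26 = 0.588. At one-sided 0.05 (t = 1.708), the observed difference must be below about 2 − 1.00 = 1.00. At one-sided 0.025 (t = 2.06), it must be below about 2 − 1.21 = 0.79.
- SD 2: the standard error is 0.392. The limits are about 1.33 and 1.19.

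Simulation of 100,000 trials with three inert cannulas gives the share in which both new cannulas pass against legacy:

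| SD of paired difference | one-sided 0.05 | one-sided 0.025 |
|---|---|---|
| 3 | 83% | 68% |
| 2 | 99.8% | 99% |

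Inert cannulas would usually be declared equivalent.

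**Step 3: what a legacy check can do.** Power of the paired change from baseline to therapeutic characterization (two-sided 0.05, n=26):

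| True legacy change | SD 3 | SD 2 |
|---|---|---|
| 2 | 90.4% | 99.8% |
| 1.5 | 69% | 96% |
| 1 | 37% | 69% |

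With no true change, the check is passed in the direction of improvement about 2.5% of the time. The 95% half-width at SD 3 is 2.06 × 0.588 = 1.21 points.

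**Step 4: limits of the check.**

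- *Patients already on HVNI at the Phase 1 baseline.* For them the change does not measure relief. If they are pooled and their change is zero, power for a true relief of 2 at SD 3 falls to about 65% if 25% of patients are on HVNI, and to 34% if 50% are (fractions assumed). If they are analysed separately, power depends on who remains. With 20 patients, noncentrality is 2/(3/√20) = 2.98 and power is 81%. With 13, it is 2/(3/√13) = 2.40 and power is 60%.
- *Improvement without a device effect.* If an inert legacy cannula is accompanied by an assumed 1-point fall from expectation or regression to the mean, it passes 37% (SD 3) to 69% (SD 2) of the time.

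**The case against.** The best defence is that the procedures make an ineffective legacy phase unlikely. Section VI titrates HVNI in Phase 1 towards relief of perceived dyspnea. The therapeutic reading is taken once a skilled clinician judges the settings to be working. Section II points to published outcomes for the legacy design. Pauses run until dyspnea has returned to baseline, and the later baselines are recorded. These points stand as mitigation. But the judgment is an unblinded bedside trigger rather than an analysis criterion, and the published data come from elsewhere. None of this shows that RPD fell on legacy in these patients.

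It may also be said that testing all applicable variables could cover a within-phase comparison. It could, so it would be wrong to say that the trial cannot examine relief. What is missing is a named analysis and its link to the conclusion.

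Four stronger readings are tempting and are not supported:

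- *Section X concedes that the cannulas do nothing in so short a time.* The sentence sits beside one about direct health benefit from participation and can be read as meaning lasting benefit. It is in tension with Section VI but does not contradict it.
- *The chance that inert cannulas escape a significant difference measures the defect.* Both legacy contrasts are non-significant in about 91% of trials, but that figure is the same if all three cannulas work equally well. It also presumes that non-significance will be read as comparability, a rule the plan does not state.
- *Unicorn is rated at half flow, so insensitivity guarantees success.* Half the Phase 1 flow is a starting reference. Section VI allows the flow to be raised and acclimatization repeated when relief is judged not comparable, and testing lower flow is a stated goal in Section I.
- *A significant fall on legacy would prove relief, and its absence in all patients would void the trial.* Neither holds, for the reasons in step 4 of the working. An observed fall of about 1.3 could also exclude zero while lying below the plan's own important difference of 2.

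**Conclusion.** The concern holds as a gap in the analysis plan. Section II promises equivalence in relieving dyspnea, while Section VIII neither names a legacy baseline-to-therapy analysis of RPD nor makes the claim depend on one. The missing margin is a separate defect, and supplying it would not close this gap: inert cannulas would pass both equivalence tests in 68% to 99.8% of trials across the SDs and alpha levels examined. Those figures rest on an illustrative margin of 2, n=26, normal errors and the plan's SD range.

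The documents do not show that the cannulas are ineffective or that RPD will fail to move. They show only that the plan would not notice if that happened. A legacy check closes the gap in part. Failing it should restrict the claim. Passing it is necessary but not sufficient, because legacy always comes first, ratings are unblinded, and entry at a Borg score of 3 or more invites regression to the mean. The sponsor should make the change; it is not a reason to hold the trial.

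**What to change.** Add to Section VIII:

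1. The paired RPD change on legacy from Phase 1 baseline to therapeutic characterization, with a 95% interval, in patients not on HVNI at that baseline. Patients already on HVNI are reported separately, with their number.
2. A rule for the conclusion. If the interval does not exclude zero in the direction of improvement, the report states that scores were similar and does not claim comparable relief of dyspnea.
3. As support, the same change for each test cannula and the RPD at the Phase 2 and 3 baselines, to show whether dyspnea returned. A patient whose current therapy is HVNI may be on it at those baselines too, and should be identified there.
4. A statement that passing is necessary but not sufficient, for the reasons given in the verdict.

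The cost is SAP wording. RPD is already collected at these points, though HVNI status at each baseline must be captured explicitly. No patients or visits are added, and clinical management is unchanged. The downside is that the relief claim may have to be withheld. At n=26 and SD 3, power is 90.4% for a legacy change of 2 but 37% for a change of 1, and it falls further as patients on HVNI at baseline are set aside.

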## HVNI Cannula Efficacy in Relieving Dyspnea

Confidential

## **III. Subject Selection**

Subjects will be identified and recruited by study investigators. The study will take place in an inpatient setting sufficient to support patients presenting with hypercapnic respiratory failure. Testing during this study will be performed in the presence of health care professionals who will provide appropriate supervision and staff training to maintain patient safety. The test will evaluate patient dyspnea, vital signs, ventilation, and oxygenation for each cannula design tested. Initial patient contact will be made by study investigators. Participants may or may not decide to enroll in the study after being consented.

## **Inclusion Criteria**

- 1. Adults, 18 years or older
- 2. The cannula prong(s) (Unicorn and Prosoft) will fit the nostril(s) so that the cannula prongs will not occlude more than 50% of the available nostril aperture of any single nostril accommodating a cannula prong.
- Demonstrated dyspnea at baseline, established by patient OR clinician assessment (see below)

   Borg Rated Perceived Dyspnea (scale 0-10) of 3 or higher

4. Severe patient baseline hypercarbia/hypercapnia of 50 mmHg or higher as measured by TcPCo2 or arterial or venous blood gas

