Ventilatory Work Effort / Work of Breathing (WOB): The physical, physiologic muscular demands of breathing manifested through signs and symptoms of increased physical exertion, manifested through pulmonary changes leading to the use of accessory muscles for inspiration or exhalation.

Fraction of inspired oxygen (FiO2; %): The percent of the delivered respiratory gas mixture that is oxygen, expressed as a fraction.

Ventilatory Rate (Respiratory Rate; RR, BPM): The number of breaths a subject takes per minute (breaths·min).

Blood Pressure (BP): as measured by systolic and diastolic pressures of the blood contained in the circulatory system, measured for this study in mmHg.

Heart Rate (HR): The number of heart beats per minute (beats·min).

Modified Borg Scale (Borg): Dyspnea is an important measure of patient respiratory distress & pulmonary functional status. The rate of perceived dyspnea (RPD) is determined by patients and clinicians to using specific descriptors, on a scale of 0 (no dyspnea) to 10 (unbearable dyspnea). The modified Borg scale is additionally used for rating the subjective perceived exertion (RPE) during exercise, while at the same workload.

Standard of Care (SOC): Site standard practices for the medical care of patients presenting with specific symptoms.

Case Report Form (CRF): The form used to record pertinent patient data to address the study aim. CRFs do not contain patient names or medical record numbers; rather they will be coded with a patient number and the site principal investigator at each center will maintain the key. The CRFs are the property of Vapotherm.

Transcutaneous  $CO_2$  (TcPCO2): This non-invasive method of measuring circulating  $CO_2$  transdermally, indicating trends for arterial carbon dioxide levels using a locally heated electrochemical sensor applied to the skin, can be used to assess a patient's adequate ventilation and oxygenation.

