## Phase 1 - Conventional Legacy cannula design (Control)

This test session is represented by Phase 1 in Figure 1, where the patient is placed on HVNI therapy with an appropriately fitted conventional legacy cannula design. Phase 1 will follow four distinct segments: (1) baseline characterization, (2) therapy acclimatization, (3) therapeutic characterization, (4) patient and clinician assessment scores. After Phase 1 is completed the next generation cannula test #1 will be able to start, as deemed appropriate by the clinician.

Baseline Characterization will be performed just prior to the therapy acclimatization segment of this Phase. If there is a reason the clinician does not deem the patient appropriate for the study, per inclusion/exclusion criteria, they may stop procedures during baseline characterization. The inpatient may be sitting or lying down in a comfortable environment. The patient will be set up and prepared for the cannula testing with appropriate data recording devices. While subject is at rest, the following data will be collected (see Table 1): RR, HR, BP, SpO2, TcPCO2 and RPD (Modified Borg scale 0-10). For the RPD, the clinician will record patient scores. The patient may or may not be on HVNI therapy at this time. The Phase 1, baseline characterization will include recording data while the patient is in an uncompromised state (e.g. ON current oxygen therapy, if applicable).

Therapy acclimatization (5 – 10 minutes) will be performed immediately after the baseline characterization segment is complete, and in accordance with site standard of care practices to maintain patient safety. The patient will be fitted with appropriately sized nasal cannula from the conventional legacy design (not to exceed 50% occlusion of the nares). Patients will be notified of best practice for the therapy, and clinicians will record whether patients prefer to keep their mouths open or closed. The acclimatization segment is the interval during which HVNI is to be titrated to provide the patient the appropriate settings for effective HVNI therapy. After the final FiO2/Flow settings are implemented and the patient is acclimatized the following data will be collected (see Table 1): RR, HR, BP, SpO2, TcPCO2 and RPD (Modified Borg scale 0-10). For the RPD, the clinician will record patient scores. Effective flow is recorded.

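### Entry can rest on the clinician's Borg rating while the primary endpoint is the patient's own score, so patients near the scale floor can enter and bias the cannula comparison towards no difference.

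*Combined protocol and SAP*

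**What the plan says.** Under III. Subject Selection, Inclusion Criteria, the third criterion reads "Demonstrated dyspnea at baseline, established by patient OR clinician assessment (see below". The only threshold beneath it is "Borg Rated Perceived Dyspnea (scale 0-10) of 3 or higher". The Glossary supports reading this as open to either rater: "The rate of perceived dyspnea (RPD) is determined by patients and clinicians to using specific descriptors".

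The endpoint belongs to the patient. II. Overall Study Objective, Aim #1 states: "The primary endpoint is the patient's targeted relief of dyspnea, as measured by the modified Borg scale (rated perceived dyspnea [RPD". In VI. Study Procedures, the clinician only writes the score down: "For the RPD, the clinician will record patient scores". The same instruction appears for Phase 2, and Phase 3 repeats the Phase 2 procedures.

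V. Subject Enrollment, Sample Size sets the scale of effect: "Estimated minimal clinical important difference of dyspnea was determined to be a difference value of 2 in modified Borg for dyspnea".

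The protocol does not require the patient's own Phase 1 baseline score to reach 3, and it does not ask which rater qualified the patient. VIII. Statistical Analysis plans neither an adjustment for baseline score nor an analysis by it.

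**The concern.** A patient who scores their own dyspnea at 1 is eligible if the clinician scores it at 3. The Borg scale stops at 0, so complete relief for that patient is a 1-point fall, half the difference on which the sample size rests. A cannula that does nothing and a cannula that relieves fully can differ by no more than 1 point in that patient. The crossover does not cure this, because the within-patient difference is the quantity being compressed.

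The direction matters. The hypothesis in II. Overall Study Objective is that the new cannulas are comparable to legacy, and the endpoints are meant to establish equivalence. VIII. Statistical Analysis, however, tests for a difference at 0.05, and no equivalence margin is given. Under that plan, lost sensitivity is liable to be read as support for the hypothesis.

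**Working it through.** **Plan's own figure.** The inputs are in V. Subject Enrollment, Sample Size: a paired t-test "with an expected difference of 2, and an expected standard deviation of 3", 90% power and alpha 0.05. Taken as two-sided with the noncentral t distribution, n = 26 gives 90.4% power. The stated 26 reproduces, so the arithmetic is not at fault. It does presuppose that an average difference of 2 points is attainable.

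**Bound on the difference.** Let b be the patient's own baseline score, taken as the same before each cannula. If the test cannula neither relieves nor worsens, the patient stays at b on test. On legacy the score cannot fall below 0. The test-minus-legacy difference is therefore at most b. At b = 2 it can just reach 2; at b of 1 or less it cannot.

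Let q be the share of patients with b of 1 or less, and let the rest show a true 2-point deficit:

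- b = 1: mean difference at most 2(1 − q) + q. At q = 25%, 1.50 + 0.25 = 1.75. At q = 50%, 1.00 + 0.50 = 1.50.
- b = 0: mean difference at most 2(1 − q). At q = 25%, 1.50. At q = 50%, 1.00.

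**Effect on power at n = 26.** Let the low group show an average difference d of 0 or 1. The overall mean difference is 2(1 − q) + qd. The SD is either held at 3, or the low group is given an SD of 1, so that the overall SD is √[9(1 − q) + q + q(1 − q)(2 − d)²]. The values of q, d and the low-group SD are assumptions.

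| q | Mean difference (d = 0 to 1) | Power, SD 3 | Power, low-group SD 1 | n for 90% power, SD 3 |
|---|---|---|---|---|
| 0 | 2.00 | 90% | 90% | 26 |
| 20% | 1.60 to 1.80 | 74% to 84% | 79% to 89% | 39 to 32 |
| 50% | 1.00 to 1.50 | 37% to 69% | 52% to 89% | 97 to 44 |

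**Simulation on the bounded scale.** Scores were rounded and confined to 0 to 10, with 26 patients per trial and a noise SD of 3/√2 per score. Legacy gave 2 points of relief and test gave none. The low group self-rated 0 to 2 and the others 3 to 8, evenly spread. These settings are also assumptions.

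| Share self-rating 0 to 2 | Mean difference | Power (t-test) |
|---|---|---|
| 0 | 1.86 | 89% |
| 20% | 1.68 | 86% |
| 50% | 1.42 | 83% |
| 100% | 1.00 | 76% |

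The estimated difference shrinks steadily in every version. The loss of power ranges from slight to severe, depending on how much the spread of scores shrinks as well.

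**The case against.** The best reply has four parts.

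- **No such patient is shown to enrol.** This stands as a limit on size: q is unknown. It does not alter what the criterion permits.
- **Sites may read the criterion as the patient's score.** The single threshold concerns perceived dyspnea, the Phase 1 baseline collects the patient's score, the clinician may stop there on eligibility grounds, and exclusion criterion 10 allows removal of unsuitable patients. These checks are discretionary. A patient who self-rates 1 and is rated 3 by the clinician meets the criterion as written, so an eligibility check has no cause to stop them.
- **The rater is not the only route to a low baseline.** At the Phase 1 baseline, "The patient may or may not be on HVNI therapy at this time". Someone who self-rated 3 at screening could score lower by then. This is true, and it favours applying the threshold at that baseline.
- **The larger fault lies elsewhere.** A false conclusion of comparability would come mainly from a difference test without a margin. This stands. The floor adds to that fault and would outlast its repair, since a diluted mean difference also falls more easily inside whatever margin is chosen.

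A reader might go further and infer that this criterion would make any cannula look comparable. The documents do not support that. The floor limits only downward movement, so a cannula that worsens dyspnea can still raise a low score. At modest shares much of the power remains: 86% against 89% in the simulation at a 20% share.

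**Conclusion.** The mismatch between the rater at entry and the rater of the endpoint is plain in the text, and nothing in the protocol closes it. Its effect is a bias towards no difference for a cannula that merely fails to relieve.

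The size is conditional. With self-ratings of 1 or less in a share q and a true 2-point deficit in the rest, the mean difference is at most 1.75 at q = 25% and 1.50 at q = 50%. At a 20% share, power lies between 74% and 89% across the assumptions tried, against 90% planned. Neither q nor the self-rated baseline distribution is in the documents, so these figures show a range and do not predict what the trial will find. The point should be corrected because the remedy is simple, but it ranks below the missing equivalence margin.

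**What to change.** Amend the third inclusion criterion to require the patient's own RPD to be 3 or higher at the Phase 1 baseline characterization. This is the same rater and scale as the endpoint, and the reading is already taken before the Phase 1 legacy cannula is fitted. Keep the clinician's rating as a pre-screen only. Define patients who do not meet the threshold as screen failures who do not count towards the 32. Without that rule, q = 25% would leave 32 × 0.75 = 24 patients, below the planned 26 before any other loss.

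If the clinician route is kept, record on the CRF which rater qualified each patient, and prespecify an analysis of the primary comparison in patients whose own Phase 1 baseline RPD is 3 or higher.

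The cost grows with q. To have 32 patients qualify, 32/(1 − q) must be assessed: 43 at q = 25% and 64 at q = 50%. Under the alternative, the restricted analysis would keep about 26 × 0.75 = 19.5, so 19 or 20, of 26 evaluable patients at q = 25%, and 13 at q = 50%. No new measurement is needed for the main fix.
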